1. PROTOCOL SUMMARY

Questions addressed

Our aim is to perform a randomized, prospective, pilot study comparing the use of coils versus vascular plugs for proximal splenic artery embolization in the setting of high-grade splenic trauma.

The questions addressed in this trial include:

1. Is it feasible to perform this type of study in this patient population by meeting patient accrual goals and obtaining adequate patient follow-up?
2. What are the clinical, technical, and economic outcomes associated with proximal splenic artery embolization using coils or vascular plugs?

Study population

Inclusion criteria: ≥18 years of age; trauma resulting in grade III or higher splenic injury on contrast-enhanced CT as defined by the AAST guidelines; splenic injury to be treated by non-operative management as decided by attending trauma surgeon and interventional radiologist; patient will undergo proximal splenic artery embolization as decided by the attending interventional radiologist

Exclusion criteria: inability to obtain informed consent; uncorrectable coagulopathy; patient is immunocompromised; pregnant; breast-feeding; non-English speakers; prisoners

Interventions

Patients will be screened for eligibility. Eligible patients will be referred for proximal splenic artery embolization and randomized to coils versus vascular plugs. Proximal splenic artery embolization will be performed. Relevant data from patient arrival and hospitalization will be collected. CT scan over-read will be performed by an attending abdominal radiologist. Follow-up data at approximately 30 days will be obtained (see

sections 6 “Patients, Recruitment, and Randomization”, 7 “Interventions”, and 9 “Data Collection”).

Outcome assessment

We plan to demonstrate the feasibility of performing this type of study in this patient population by meeting patient accrual goals and obtaining adequate patient follow-up. Secondarily, we will assess outcomes of both groups using technical success (ability to embolize the mid-splenic artery with the prescribed device), device failures, intra-procedural complications, procedural time, equipment costs, radiation exposure, need for secondary embolic agents, length of stay, post-embolization transfusion requirements, delayed complications, and splenic salvage rates as secondary endpoints.

Trial coordination

[name] and [name] will be principle investigators. [name] will be program manager.

3. INTRODUCTION/ BACKGROUND

Trauma is the leading cause of death and disability in the United States for all age groups and the single most important cause for years of life lost for persons under the age of 65 [1]. As a major, urban, academic medical center, UAB Hospital is one the busiest trauma centers in the country treating approximately 4,500 major trauma patients annually. Many of these patients present with significant abdominal injuries. Major abdominal trauma, whether by blunt forces or penetrating injuries, carries a significant risk for patient mortality. The spleen is one of the most commonly injured organs in abdominal trauma [1]. Hemodynamically unstable patients whose primary site of injury is the spleen require splenectomy. However, the management of hemodynamically stable patients with traumatic injuries to the spleen is less well-defined. The recognition of the key role of the spleen in producing antibodies, monocytes, and activated lymphocytes has led to a paradigm shift in the management of splenic injuries towards preservation when possible. Currently, the majority of patients with splenic injury are managed without surgery [8].

Splenic preservation rates are improved for patients with high-grade splenic injuries when NOM is supplemented by image-guided, trans-catheter splenic artery embolization (SAE) [3-6]. SAE is currently the standard of care for hemodynamically stable patients with high-grade splenic injuries. SAE is primarily performed using proximal splenic artery embolization (pSAE). pSAE is most often accomplished using either coils or vascular plugs as the embolic agent, both of which are FDA-approved.

Coils have a long history of efficacy and safety for embolization and are thus familiar embolic agents to most endovascular specialists. Further, coils large enough to embolize the mid-splenic artery can be deployed through a standard micro-catheter, which means they can be used in even the most tortuous splenic arteries. However, multiple coils may be needed in the same patient to achieve hemostasis in the mid-splenic artery. This attribute may increase overall cost, iodinated contrast use, procedural time, and the radiation exposure to the patient and medical staff. Additionally, given the high-flow nature of the splenic artery, even an appropriately sized coil may migrate distally. Some of these limitations are overcome through the introduction of coils that are both longer

and larger than traditional coils, namely POD® coils (Penumbra, Alameda, CA, USA). Using these larger coils can decrease the number needed to obtain hemostasis. These coils come in two varieties: 1) a helical coil sized to the vessel diameter that anchors the coil pack in the high-flow vessel thereby reducing the risk of distal migration and 2) a packing coil that is used to fill in the spaces within the helical coil. A typical pSAE using coils will involve the deployment of one helical coil followed by multiple packing coils until hemostasis is achieved.

Vascular plugs attempt to overcome the limitations of coils. For example, the deployment of a single vascular plug can typically provide hemostasis in the mid-splenic artery, theoretically reducing procedural time, contrast load, and radiation exposure. Despite this, vascular plugs are usually less familiar devices to endovascular specialists. Another drawback of vascular plugs is that they cannot be deployed through a standard micro-catheter but rather require the advancement of a larger, stiffer 0.035 inch system into the mid-splenic artery. This may limit their use in very tortuous splenic arteries. Vascular plugs reaching up to 8mm in size (Amplatzer™ IV, Abbott Medical, Abbott Park, IL, USA) can be deployed through a standard 5F diagnostic catheter. Larger vascular plugs (Amplatzer™ II) require at least a larger 6F guiding catheter.

Currently, the selection of embolic agent for pSAE is primarily based on operator experience and preference. The efficacy, technical success, and cost of using coils compared to vascular plugs has been evaluated in such conditions as pelvic congestion syndrome [10], yet, to the best of our knowledge, these embolic agents have never been compared for their use in pSAE, much less in a randomized, prospective fashion. We anticipate this pilot trial to demonstrate the feasibility of a larger study and provide sufficient information to identify appropriate primary endpoints. The innovation of this proposal is strengthened by the inclusion of over-reads of pre-procedural CT scans, which will allow accurate grading of splenic injury and information regarding associated vascular injury to the spleen. If found, significant differences between our study groups in either clinical outcomes, technical parameters, or cost would have an immediate impact on how we care for trauma patients both locally and nationally.

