8. OUTCOMES

Aim 1: Demonstrate feasibility by meeting enrollment and follow-up goals.

Objective 1a: Enroll at least 50% of eligible patients (50 patients total; 25 patients per arm)

Objective 1b: Obtain follow-up in at least 80% of enrolled patients

Aim 2: Assess for similarities and differences between the groups regarding clinical outcomes.

Objective 2a: Compare clinical outcomes of pSAE using coils versus vascular plugs (splenic salvage, immediate/delayed complications, patient length of stay, and post-embolization transfusion requirements)

Objective 2b: Compare technical outcomes of pSAE using coils versus vascular plugs (technical success (defined as the ability to access and embolize the mid-splenic artery), intra-procedural complications, necessity of a secondary embolic to obtain satisfactory hemostasis, and intra-procedural radiation doses)

Objective 2c: Conduct cost analysis of using coils versus vascular plugs (room time, equipment such as catheters, wires, and sheaths, and the cost of the embolic agent itself)

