9. DATA COLLECTION

Data is abstracted into an electronic case report form (eCRF) by study staff. The eCRF uses the Research Electronic Data Capture (REDCap) system, a secure research database developed by the NIH. A full list of variables to be collected is shown below. Data logic checks are used to minimize data entry errors.

The following admission parameters will be collected:

- a) Source of patient (transferred from another facility or from the scene of injury?)
- b) Mechanism of injury
- c) Date and time of arrival
- d) Vital signs (temperature, heart rate, blood pressure, respiratory rate)
- e) Use of vasopressors at time of arrival
- f) Intubated at time of arrival
- g) Glasgow Coma Scale (GCS)
- h) Injury Severity Scale (ISS)
- i) Undergoing massive transfusion protocol?

The following blood tests, which are all measured routinely as part of the clinical assessment of trauma patients, are collected, as soon as possible upon arrival:

- a) Arterial blood gas
- b) Hemoglobin and hematocrit
- c) Platelet count
- d) Coagulation parameters including prothrombin time (PT), international normalized ratio (INR), activated partial thromboplastin time (APTT), and Anti-Xa
- e) Thromboelastograph (TEG) or thromboelastogram (ROTEM)

The following data points will be extracted from the initial CT report (emergent):

- a) Phase of enhancement
- b) Splenic injury grade according to AAST guidelines

- c) Signs of accompanying vascular injury such as pseudoaneurysm, extravasation, arterio-venous fistula, or hemoperitoneum
- d) Presence or absence of other intra-abdominal or extra-abdominal trauma

The following data points will be collected from the embolization procedure:

- a) Duration
- b) Radiation dose
- c) Contrast type and volume
- d) Splenic artery diameter
- e) Presence of pseudoaneurysm, arterio-venous fistula, or contrast extravasation on angiography
- f) Embolization material
 - a. Primary (coils vs. vascular plugs)
 - b. Secondary (beads, coils, vascular plugs, foam, other)
- g) Technical success
- h) Intra-procedural complications (non-target embolization, migration of the coil or vascular plug, ineffective treatment requiring splenectomy, vessel rupture, injury at the access site, and splenic infarction/abscess)

The following data points will be collected from the over-read of the CT (non-emergent):

- a) Phase of enhancement
- b) Splenic injury grade according to AAST guidelines

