11. STATISTICAL ANALYSIS

As stated, the primary outcome of this study is to demonstrate the feasibility of performing this type of trial in this patient population.

As a secondary aim, we anticipate being able to identify potential variables as primary endpoints for a larger study.

The principle investigators, project manager, and research coordinator will have access to data. Statistical analysis will be performed by [name].

Continuous variables will be compared using the Student's t-test. Categorical statistics will be compared using Chi-squared probability testing with Fischer exact modification when warranted by frequency observed. Both univariate and multivariate Cox models will be examined to determine the ability of clinical variables to predict the likelihood of clinical success or failure (i.e splenic salvage). A pre-determined p value of 0.05 was considered the threshold for statistical significance.

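### Radiation dose is compared between arms without adjustment and no body-size measure is listed for collection, so a valid comparison gives up precision that could be recovered cheaply

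*Combined protocol and SAP*

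**What the plan says.** Section 3 gives radiation as one of the ways in which the devices may differ. Of the need for several coils it says: "This attribute may increase overall cost, iodinated contrast use, procedural time, and the radiation exposure to the patient and medical staff". Of the single plug it says that it works by "theoretically reducing procedural time, contrast load, and radiation exposure".

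Radiation is then carried into the outcomes. The Protocol Summary lists "procedural time, equipment costs, radiation exposure, need for secondary embolic agents" among the secondary endpoints, and section 8, Objective 2b, ends its technical outcomes with "necessity of a secondary embolic to obtain satisfactory hemostasis, and intra-procedural radiation doses".

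Section 9 introduces its variables with "A full list of variables to be collected is shown below". The nearest admission item to a body measurement is "Vital signs (temperature, heart rate, blood pressure, respiratory rate"); weight, height and BMI do not appear. The procedure items include radiation dose (with no dose quantity named), duration, contrast volume and splenic artery diameter, but no fluoroscopy time.

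Section 11 says "Continuous variables will be compared using the Student's t-test". Its only multivariable models are Cox models for splenic salvage. Section 6.4 describes sealed numbered envelopes and mentions no stratification.

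**The concern.** For a given procedure, x-ray output generally has to rise with the thickness of the patient, so part of the patient-to-patient spread in dose probably reflects body size and not the device. The documents neither state nor quantify this. If it is so, an unadjusted comparison leaves that part of the spread in the error term, although body size is fixed before randomization and easy to record.

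The stake is Aim 2, which is to identify endpoints for a larger trial. Judging dose as a candidate needs an estimate of the device difference that is as sharp as 50 patients allow. It also needs an estimate of the residual spread that the larger trial would face. Without a body-size variable, the pilot yields only the unadjusted spread and cannot show how much smaller a trial with adjustment could be.

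**Working it through.** **The plan's own figure.** Section 10: about 100 embolizations in 12 months, of which 50% are to be enrolled. 0.50 × 100 = 50, and 50 / 2 = 25 per arm. This reproduces. It is an accrual target; the documents give no effect size, SD or power for radiation dose.

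**Inputs from the documents.** n = 25 per arm; significance threshold 0.05 (taken as two-sided, since section 11 does not say).

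**Assumed inputs, not in the documents.** SD of log dose 0.7 (range 0.6-0.8); true dose reduction of 30%; share of log-dose variance explained by body size, R², 0.2 to 0.5.

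**Formulas.** Standardized difference d = |ln 0.7| / (SD × √(1 − R²)), with |ln 0.7| = 0.357. Power is that of a two-sample t-test at 25 per arm. Equivalent unadjusted sample size = 25 / (1 − R²).

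**Results at SD 0.7.**

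| R² | residual SD | d | power | equivalent n per arm |
|---|---|---|---|---|
| 0 (unadjusted) | 0.70 | 0.51 | 42% | 25 |
| 0.20 | 0.63 | 0.57 | 51% | 31 |
| 0.35 | 0.56 | 0.63 | 59% | 38 |
| 0.50 | 0.49 | 0.72 | 70% | 50 |

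**Sensitivity to the SD.** Unadjusted power is 54% at SD 0.6 and 34% at SD 0.8. Adjusted power over R² 0.2 to 0.5 is 63-83% at SD 0.6 and 41-59% at SD 0.8. Adjustment helps at every setting in the range.

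**Without assuming an SD for dose.** The difference detectable with 80% power, by the normal approximation, is (1.96 + 0.84) × √(2/25) = 0.79 SD unadjusted. Multiplied by √(1 − R²), it becomes 0.71 SD at R² = 0.2 and 0.56 SD at R² = 0.5.

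**What it means for the larger trial.** To detect 0.5 raw SD with 80% power takes 63 per arm unadjusted, 51 at R² = 0.2 and 32 at R² = 0.5. The pilot as written cannot say where in that range the larger trial would fall.

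**Validity of the unadjusted test.** In simulation (10,000 trials per setting, 25 per arm, R² from 0 to 0.6), the unadjusted t-test rejected a true null in 4.8% to 5.3% of trials, and its mean estimate matched the true difference. For a true 0.5 SD difference, power was 41% by t-test, against 48%, 60% and 78% with body size as covariate at R² = 0.2, 0.4 and 0.6.

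**Chance imbalance.** The between-arm difference in mean body size has a standard error of √(2/25) = 0.283 SD, so an imbalance above 0.5 SD in either direction has probability of about 8%. With SD 0.7 and no device effect, an imbalance of exactly 0.5 SD would show as an expected dose ratio of exp(0.7 × √R² × 0.5), that is 1.17 at R² = 0.2 and 1.28 at R² = 0.5.

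**The case against.** The strongest reply is that an unadjusted comparison of randomized arms is valid and that covariate adjustment is an efficiency choice. Dose is one of about eleven secondary endpoints in a study whose primary outcome is feasibility and whose size comes from accrual, so low power for it is expected. Even with adjustment, 51-70% power would not support a pass-or-fail reading. All of this stands, and it sets the weight of the point.

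Two further replies stand in part. Duration and contrast volume are collected, and section 7.3 has time to hemostasis recorded, so dose would not be read alone; but none of these measures beam-on time or body size. Section 9 is also not strictly complete: time to hemostasis is to be recorded under section 7.3 and costs are an outcome in section 8, yet section 9 lists neither. Absence from the list is therefore weaker evidence than the word full suggests, although nothing elsewhere provides for weight or height.

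A reader might infer more than the documents support:

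- *That body size dominates the spread of dose.* No figure in the documents shows this, and the range assumed here leaves 50-80% of the variance to other causes.
- *That the plan invites false-positive findings.* Randomization prevents this. Chance imbalance is already counted in the 5%; a large imbalance in one realized trial could mislead, but that is not a bias in the design.
- *That an imbalance could never be examined later.* Data are abstracted from medical records at a single center, and every patient has a CT scan, so body size could probably be retrieved for 50 patients. What would be lost is prespecification.

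**Conclusion.** The point holds as one of precision. Radiation dose is a hypothesized device difference and a secondary technical outcome, yet no body-size measure is listed and the planned test is unadjusted. The comparison is unbiased with correct type I error. It forgoes a gain from about 42% to 51-70% power, equivalent to 31-50 patients per arm instead of 25. It also leaves the adjusted residual variance unknown when dose is judged as an endpoint for the larger trial.

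The gain depends on an assumed log-dose SD of 0.7, a true 30% reduction and an R² of 0.2 to 0.5, none of which comes from the documents. If body size explained little of the spread, the gain would be small. The primary feasibility outcome is untouched. This is a cheap improvement to consider, not a flaw that undermines the study.

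**What to change.** In section 9, add weight and height to the admission list (from the chart or anesthesia record) and fluoroscopy time to the procedure list (from the machine dose report). State which dose quantity is to be recorded.

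In section 11, prespecify for this outcome: *Log radiation dose will be analyzed by linear regression on randomized arm with weight (or BMI) as covariate; the adjusted dose ratio will be reported with its 95% confidence interval, and the residual SD with and without the covariate. Fluoroscopy time will be reported by arm alongside.* Choose weight or BMI before the data are seen. Fluoroscopy time should not itself be a covariate, because it arises after randomization and may carry part of the device effect.

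The cost is three extra eCRF fields from existing records and a short addition to section 11, with no added patients or visits. Some weights in trauma patients will be estimated, not measured, which reduces the gain.

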7.2 Vascular plugs

Vascular plugs are FDA-approved endovascular occlusion devices that require an 0.035 inch system within the splenic artery for deployment (Figures 2 and 3). The Amplatzer™

IV vascular plug can be deployed through a traditional 5F diagnostic catheter. However, the largest Amplatzer™ IV vascular plug is only 8 mm in size, which may be too small for some splenic arteries. In these cases, a larger Amplatzer™ II vascular plug is needed although these vascular plugs require a larger system for deployment.

[figure not shown]

Figure 2. Picture of an
Amplatzer™ IV VP (from St. Jude
Medical)

[figure not shown]

Figure 3. Picture of an
Amplatzer™ II VP (from St. Jude
Medical)

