Local anesthesia will be achieved with lidocaine. The right common femoral artery is the most commonly used vascular access for splenic artery embolization but the left common femoral artery may be used for certain patients. No radial artery access will be used. Regardless, the artery is accessed under direct sonographic guidance with a micro-puncture set. The micro-puncture set is then exchanged for a vascular sheath over a wire and attached to a heparinized saline flush. A celiac axis angiogram is then performed. The attending interventional radiologist will choose the diagnostic catheter based on his/her preference. The attending interventional radiologist will review the celiac angiogram to identify an appropriate landing zone in the mid-splenic artery distal to the origin of the dorsal pancreatic artery but proximal to the origin of the pancreaticomagna artery in order to preserve collateral flow to the spleen via the transverse pancreatic artery. The vessel's diameter at this location will be measured and recorded. For patients randomized to coil embolization, a high-flow micro-catheter is navigated to the location of embolization with the assistance of a micro-wire. The micro-wire-micro-catheter combination will be left to the discretion of the attending interventional radiologist. Once the micro-catheter is in place, a splenic angiogram will be performed. Coil embolization will then proceed per the manufacturer's instructions for use until satisfactory hemostasis is achieved. For patients randomized to vascular plug embolization, the appropriately-sized catheter or sheath is advanced to the location of embolization. The tools used to access the mid-splenic artery will vary depending on the operator's experience and patient anatomy. Once the catheter is in place, a splenic angiogram will be performed. Vascular plug embolization will then proceed per the manufacturer's instructions for use until satisfactory hemostasis is achieved. For both coil and vascular plug embolization, absence of flow at the level of the embolic agent in the mid-splenic artery will serve as the endpoint for satisfactory hemostasis. Regardless of the embolic used the interventional radiologist will perform intermittent angiograms (one per minute) to determine if stasis has been achieved. The time to hemostasis will be recorded. If hemostasis is not achieved after 15 minutes, then a secondary embolic can be employed. If a secondary embolic agent such as particles or gelfoam is needed for patients in either group, this will be recorded. All potential secondary embolic agents are FDA-approved devices and commercially available. Additionally, if the operator is unable to navigate into the mid-splenic artery with the necessary tools to perform the

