
required embolization, this will also be recorded. In this circumstance, the procedure will be recorded as a technical failure and the operator will then proceed to treat the patient as he/she deems appropriate. Catheters and wires will be removed after hemostasis is obtained in the mid-splenic artery. As is standard at our institution, the arteriotomy will be closed with a FDA-approved, commercially available vascular closure device, if possible. If the patient isn't a candidate for a vascular closure device, then hemostasis at the arteriotomy will be obtained with manual pressure, as is standard at our institution.

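### Splenic artery diameter is measured but not used to sharpen the device comparisons, and tortuosity is not recorded at all: a loss of precision and of planning information, not a bias

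*Combined protocol and SAP*

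**What the plan says.** **Anatomy and device.** Section 3 says coils pass through a standard micro-catheter, "which means they can be used in even the most tortuous splenic arteries". Plugs need a larger, stiffer system, and the same section comments: "This may limit their use in very tortuous splenic arteries". Section 7.2 notes that the type IV plug goes no larger than 8 mm, "which may be too small for some splenic arteries"; a type II plug with a larger delivery system is then used.

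**What is recorded.** Section 7.3 says of the landing zone: "The vessel's diameter at this location will be measured and recorded". Section 9 introduces its lists with "A full list of variables to be collected is shown below", and the procedure list includes "Splenic artery diameter". In the readable text, neither that list nor the CT over-read list has a tortuosity item. When the operator cannot reach the mid-splenic artery, section 7.3 says: "In this circumstance, the procedure will be recorded as a technical failure".

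**What is analysed.** Section 11 says: "Continuous variables will be compared using the Student's t-test". Categorical outcomes get chi-squared or Fisher tests. The only multivariable models are Cox models for splenic salvage, whose covariates are not named. Feasibility is the primary outcome. The device comparisons serve Aim 2, which is to identify endpoints for a larger trial.

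**The concern.** The protocol gives anatomical reasons to expect the two devices to behave differently, but its data and analysis do not follow those reasons through. Two things are at stake.

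- **Precision.** If artery diameter predicts duration, radiation dose or cost, an analysis that ignores it has a larger standard error than it needs. With 25 patients per arm that matters, and the covariate is already collected.
- **Planning information.** A failed navigation is captured, but the degree of tortuosity in all other patients, in both arms, is not. Without that denominator nobody can describe whether plug failures cluster in tortuous arteries, or whether the arms happened to differ in tortuosity. Both bear on whether the larger trial should stratify by anatomy.

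**Working it through.** **1. The plan's own figure.** Section 10 expects about 100 embolizations in 12 months and aims to enrol 50%: 0.50 × 100 = 50, and 50 / 2 = 25 per arm. This reproduces. The target rests on accrual; the documents give no power, effect size, SD or event rate for any device comparison.

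**2. Is the unadjusted test valid?** 40,000 trials were simulated with 25 per arm, no device effect, and a baseline covariate explaining 0, 20 or 40% of outcome variance. The unadjusted t-test at two-sided 0.05 rejected in 5.0, 5.0 and 4.9% of trials, with a mean difference of about zero. Ignoring anatomy causes neither bias nor type I error inflation.

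**3. How much precision is lost?** For one covariate explaining a share R² of the variance, adjustment multiplies the variance of the arm difference by about

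f = (1 − R²) × (1 + 1/(N − 4)), with N = 50, so the second factor is 1 + 1/46 = 1.0217.

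The effective size per arm is 25 / f, and the standard error is multiplied by √f. The unadjusted difference detectable with 80% power is (1.96 + 0.84) × √(2/25) = 0.79 SD. The R² values are assumptions.

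| R² | f | SE ratio | Effective n per arm | Detectable difference |
|---|---|---|---|---|
| 0.05 | 0.971 | 0.985 | 25.8 | 0.78 SD |
| 0.10 | 0.920 | 0.959 | 27.2 | 0.76 SD |
| 0.25 | 0.766 | 0.875 | 32.6 | 0.69 SD |

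**4. How likely is a chance imbalance?** Section 6.4 describes sealed numbered envelopes, with no stratification in the readable text. Taking the number of very tortuous arteries in each arm as Binomial(25, p), the arms differ by 5 patients (20 percentage points) or more with probability 11, 16 and 19% for p = 20, 30 and 40%. The values of p are assumptions. For diameter, the standard error of the difference in means is √(2/25) = 0.283 SD, so an imbalance above 0.5 SD has probability of about 8%. A diameter imbalance could be seen in the planned data; a tortuosity imbalance could not.

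**5. What could results by tortuosity class show?** If 30% of arteries are tortuous, each arm has 0.30 × 25 = 7.5 of them. Exact 95% intervals at that size are very wide: 5 successes in 8 gives 24-91%, and 7 in 7 gives 59-100%. Across whole arms, 0/25 against 5/25 failures gives Fisher p = 0.0502. Failures will be too few to support covariate adjustment of technical success.

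**The case against.** A reader might infer that anatomy will be mistaken for a device effect. The documents do not support that. Allocation is random, so anatomy is balanced in expectation, and the error rate of the unadjusted test already allows for chance imbalance (step 2).

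A reader might also infer that the pooled plug success rate is contaminated by arteries that plugs cannot reach. Section 8 defines technical success to include access, and section 7.3 counts failed navigation as a failure. Inability to deliver the plug is therefore part of the effect of being assigned a plug, and should not be adjusted away.

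Nor does the protocol say that anatomy decides how well a device works. Its wording is tentative, and for large arteries section 7.2 describes a different plug, not an expected failure. Any figure for the gap in plug success between tortuous and other arteries would only return the rates one assumed, since the documents give none.

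Further points stand. Feasibility is primary, so the main conclusion is not at risk. The Cox covariates are unspecified, so diameter is not excluded there, although that would not help duration, dose or cost. Diameter is already collected, so adjustment stays possible later. Class-level results would be too imprecise to settle whether to stratify. These objections limit the size of the point. They do not remove the value of fixing the covariate before the data are seen, or of recording tortuosity while a reader is already examining each CT.

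**Conclusion.** The point holds as one of efficiency and missing description. The planned comparisons are valid and unbiased. Precision on duration, radiation dose and cost is given up to the extent that diameter predicts them: 25 per arm would be worth about 27-33 if diameter explains 10-25% of the variance, and less than one extra patient per arm if it explains 5%. Separately, an imbalance in tortuosity, or a device effect that differs with tortuosity, could not be seen at all.

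The R² values, the prevalence of tortuosity and two-sided testing are assumptions. The change is worth making because it costs little and serves Aim 2. It does not touch the feasibility outcome or the target of 50.

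**What to change.** 1. **Section 11.** Analyse procedure duration, radiation dose and cost by linear regression on randomized arm, with splenic artery diameter as a pre-specified covariate and a log scale where the outcome is skewed. Report the unadjusted comparison alongside.
2. **CT over-read (sections 7.4 and 9).** Add splenic artery diameter and a tortuosity grade on a fixed three-level scale, both scored from the initial CT without knowledge of arm. Use the CT diameter as the covariate where available. The angiographic diameter in section 7.3 is taken after randomization by the operator, for whom no blinding is described.
3. **Reporting.** Tabulate diameter and tortuosity by arm. Give technical success by arm within tortuosity class with exact confidence intervals, labelled descriptive. Do not adjust technical success for tortuosity.

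The cost is a paragraph in section 11 and two items on a CT read that is already planned. The downside is that the grade is partly subjective, and that class-level estimates, on about 7-8 tortuous arteries per arm if 30% are tortuous, will be very imprecise.
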